10.1 STATISTICS

10.2 Sample size

This will be a single arm, single center, open label study of the combination of vosaroxin with decitabine as an induction therapy in previously untreated patients with acute myeloid leukemia (AML) or high risk myelodysplastic syndrome (MDS) who are elderly (age \geq 60) and/or unable to tolerate standard therapy. A total of up to 84 patients will be enrolled in the study.

Phase I

A total of up to 24 patients will be accrued into the Phase I part.

Phase II

A total of up to 60 patients (including 6 patients treated at the MTD from the Phase I part) will be recruited for the Phase II part.

The primary efficacy endpoint is overall response rate (ORR). $ORR = CR + CR_p + CR_i$. Responses will be evaluated at the end of the first induction cycle and second induction cycle (if a second induction cycle is needed). With a null hypothesis of 40% historical response rate, a sample size of 60 patients would be required to demonstrate a response rate of 60% for the combination of vosaroxin and decitabine using a one-sample exact binomial test and with a two-sided alpha of 0.05 and a power of 82%.

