10.3 Statistical Design

Phase I

. In phase I portion of the study the MTD is defined as the highest daily oral dose evaluated at which $<33\%$ of patients experience a DLT. Six patients will be treated. If clinically significant drug related Grade 3-4 toxicity is observed during the first cycle in 0-1 patient out of 6 patients, this will define a safe schedule and the study will open broadly for the Phase II portion. If drug related Grade 3-4 toxicity is observed in 2 or more of 6 patients, this dose will exceed DLT, and a lower dose schedule will be investigated in an additional 6 patients. Please refer to Section 4.4. The dosing algorithm is presented in Table?.

Table 7. Dosing algorithm

Dose Level	Vosaroxin D1&D4	Decitabine
-3	50mg/mL	20 mg/m ² (Days 1-4)
-2	50 mg/m ²	20 mg/m ² (Days 1-5)
-1	70 mg/m ²	20 mg/m ² (Days 1-5)
0	90mg/m ²	20 mg/m ² (Days 1-5)

Phase II

Efficacy

The historical data suggested an ORR of 40% and with the assumption that the improved ORR is 60% the study will be stopped early if the observed patients' data suggest that:

$$\Pr(n > 0.6J \text{ data}) < 0.025$$

Here n is the overall response rate (ORR). That is, if at any time during the study we determine that there is a less than 2.5% chance that the average ORR is greater than 60%, we will terminate the study. The ORR is assumed to follow a non-informative prior of Beta (1.2, 0.8). The stopping boundaries for ORR, based on these assumptions and monitoring conditions are found in table 8. We will apply these stopping boundaries starting from the fifth patient and in cohorts of 5. For example, accrual will cease if only 2 or less than 2 patients experience overall response among the first 10 patients treated. The operating characteristics are summarized in table 8.

Table 8. Stopping boundaries for ORR

Number of patients evaluated	5	10	15	20	25	30	35	40	45	50	55	60
------------------------------	---	----	----	----	----	----	----	----	----	----	----	----

for response												
Number of patients with response (i.e., CR, CRp or CRi)	0	0-2	3-5	6-7	8-9	10-12	13-15	13-17	18-20	21-22	23-25	26-28

Table 9. Operating characteristics for monitoring of overall response rate

True overall Response Rate	Early Stopping Probability		Sample size		
			25%, 50%, 75%		
0.35	0.974		10	15	30
0.40	0.888		15	20	35
0.45	0.702		15	35	60
0.50	0.442		30	60	60
0.55	0.209		60	60	60
0.60	0.079		60	60	60
0.65	0.027		60	60	60

Toxicity Monitoring

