Following are the rules for the monitoring of toxicities in the Phase II portion of the study. Toxicity will be defined as clinically significant non-hematologic drug related grade 3 or higher adverse events. The probability of toxicity is denoted by PE. We assume PE – beta (0.6, 1.4). Our stopping rule is given by the following probability statement: Probability (PE > 0.30 | data) > 0.975. That is, we will stop the study if, at any time during the study, we determine that there is more than 97.5% chance that the toxicity is more than 30%. This stopping rule will be applied in each cohort. The stopping boundaries for clinically significant toxicities observed during the first cycle, based on these assumptions and monitoring conditions found in table 10. We will apply these stopping boundaries starting from the fifth patient and in cohorts of 5. For example, accrual will cease if 4 patients experience clinically significant toxicities during the first cycle among the first 5 patients treated. The operating characteristics are summarized in table 11.

Table 10. Stopping boundaries for Phase II toxicities

The number of patients evaluated for toxicities	5	10	15	20	25	30	35	40	45	50	55	60
The number of patients with DLTs	4	5-6	7-8	9-10	11-12	13-14	15-16	17-18	19	20-21	22-23	24-25

Table 11. Operating characteristics

True Toxicity Rate	Early Stopping Probability	Sample Size		
		25 th percentile	Median	75 th percentile
0.10	0.008	60	60	60
0.20	0.010	60	60	60
0.30	0.082	60	60	60
0.40	0.474	30	60	60
0.50	0.906	15	25	40

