10.4 Statistical Analysis Plan

All patients who received at least 1 dose of the combination therapy will be included in the intent-to-treat analysis for efficacy and safety. Demographic/clinical characteristics and safety data of the patients will be summarized using descriptive statistics such as mean, standard deviation, median and range. Response rates will be presented with 95% confidence intervals. The association between response and patient and clinical characteristics will be examined by Wilcoxon's rank sum test or Fisher's exact test. Overall survival time will be estimated using the

Kaplan-Meier method. Patients who drop out of the study will be included in the time to event data as "censored data". The two-sided log-rank test will be used to assess the differences of time to events between groups.

11.0 DATA CONFIDENTIALITY PROCEDURES:

Samples are identified by patients' unique identification number, which allows patient identification and linkage to the clinical database. Because many of these studies require clinical correlation, the medical record number (MRN) is maintained in the Oracle database. Only designated users may view data associated with patient identifiers. Other users see only a unique patient identifier. Dates of birth are not available to general users, this information is only available to central personnel and it is used to calculate age, as part of data that may be important to correlate with research assay results. This database is password-protected.

12.0 REFERENCES:

2. Kantarjian HM. Therapy for elderly patients with acute myeloid leukemia: a problem in search of solutions. *Cancer* 2007;109:1007-1010.
4. Erba HP. Prognostic factors in elderly patients with AML and the implications for treatment. *Hematology / the Education Program of the American Society of Hematology American Society of Hematology Education Program* 2007:420-428.

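### The stated 82% power is that of a fixed 60-patient test with success at 33 or more; under the plan's own futility rule it is 79.7% before any toxicity stops, and the success count is not written down

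*Combined protocol and SAP*

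**What the plan says.** Section 10.2 (Sample size, Phase II) sets the null rate and the size: "With a null hypothesis of 40% historical response rate, a sample size of 60 patients would be required". The target ORR is 60%. The method, error level and power are then given in these words: "using a one-sample exact binomial test and with a two-sided alpha of 0.05 and a power of 82" percent. The section mentions no interim look and gives no number of responders that counts as success. The 60 are described as "A total of up to 60 patients (including 6 patients treated at the MTD from the Phase I part").

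Section 10.3 (Statistical Design, Phase II) adds two stopping rules.

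- **Futility.** With a Beta(1.2, 0.8) prior, checked from the fifth patient in cohorts of 5: if "there is a less than 2.5% chance that the average ORR is greater than 60%, we will terminate the study". Table 8 gives the boundaries. Table 9 gives an early stopping probability of 0.079 at a true ORR of 60%.
- **Toxicity.** Stop if the posterior probability that the toxicity rate exceeds 30% is above 0.975. For example, "accrual will cease if 4 patients experience clinically significant toxicities during the first cycle among the first 5 patients treated". Table 11 gives early stopping of 0.010 at 20% true toxicity and 0.082 at 30%.

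Section 10.4 says of the final analysis of response only this: "Response rates will be presented with 95% confidence intervals". It names no interval method and no success criterion.

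**The concern.** A reader of 10.2 will take 82% as the chance that the trial succeeds if the true ORR is 60%. The futility rule is worded as mandatory, and some of the trials it stops at a true ORR of 60% would have gone on to reach the success count. Power must therefore be below the fixed-sample figure, and 10.2 does not say that its figure leaves interim stopping out.

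The second gap is the decision rule. The last cell of Table 8 (26-28 of 60) is a futility boundary, so the reading of 29 to 32 responders is left open. A two-sided exact binomial test at 0.05 does not settle 32 of 60, because the common definitions of the two-sided exact p-value disagree there. In an open-label, single-arm trial, that leaves the primary conclusion at 32 responders open to a choice made after the data are seen.

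**Working it through.** **Inputs.** From 10.2: n = 60, null rate 0.40, alternative 0.60, exact binomial test, two-sided 0.05. From 10.3: prior Beta(1.2, 0.8); stop if Pr(ORR > 0.60 | data) < 0.025; looks every 5 patients; the Table 8 boundaries.

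**Step 1: reproduce the 82%.** For X ~ Binomial(60, p):

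| Success if X ≥ | P at p = 0.40 | Doubled | P at p = 0.60 (power) |
|---|---|---|---|
| 32 | 0.02503 | 0.0501 | 0.8816 |
| 33 | 0.01328 | 0.0266 | 0.8221 |
| 34 | 0.00664 | 0.0133 | 0.7464 |

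The smallest count with an upper tail of at most 0.025 is 33, and only 33 gives 82%. The stated figure is correct for a fixed test.

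**Step 2: reproduce the futility boundaries.** After x responders in n patients the posterior is Beta(1.2 + x, 0.8 + n − x). The largest x with Pr(ORR > 0.60) < 0.025 at n = 5, 10, ..., 60 is 0, 2, 5, 7, 9, 12, 15, 17, 20, 22, 25, 28. These equal the upper ends of all 12 cells in Table 8.

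**Step 3: check the early stopping.** An exact recursion carries the distribution of responders forward 5 patients at a time and removes the mass at or below the boundary at each look from 5 to 55. Early stopping is 0.0815 at ORR 60% (Table 9: 0.079) and 0.8885 at ORR 40% (Table 9: 0.888). The calculation therefore represents the plan's own rule.

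**Step 4: power with the futility rule.** P(not stopped and X ≥ 33):

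- at ORR 60%: 0.7973, so the loss is 0.8221 − 0.7973 = 0.0248, or 2.5 points (a simulation of 400,000 trials gives 0.7972);
- at ORR 40%: 0.0123, against 0.0133 without the rule.

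None of the loss comes back through stopped trials: at every boundary the one-sided p-value against 40% is 0.18 or more.

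**Step 5: toxicity stops.** Assume that toxicity is independent of response, which the documents do not establish, and use Table 11:

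- 20% true toxicity: 0.7973 × (1 − 0.010) = 0.789;
- 30% true toxicity: 0.7973 × (1 − 0.082) = 0.732.

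Applying the 0.975 rule directly gives stopping of 0.0082 and 0.0833, hence power of 0.791 and 0.731. The printed counts in Table 10 were not used. From 10 patients on, the lower ends of its cells are below the counts that the 0.975 rule gives; acting on them would give stopping of 0.0458 and 0.2768, and power of about 76.1% and 57.7%.

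**Step 6: 32 of 60.**

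- Doubled tail: 2 × 0.02503 = 0.0501, not significant.
- Minimum-likelihood p-value (all outcomes no more probable than 32 under 40%): 0.0471, significant.
- Lower 95% limit: Clopper-Pearson 0.39996 (includes 40%), Wilson 0.409 (excludes it). At 33 of 60 the Clopper-Pearson limit is 0.416.

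Exactly 32 responders among 60 has probability 0.8816 − 0.8221 = 0.059 at ORR 60% and 0.02503 − 0.01328 = 0.012 at ORR 40%. Success at 32 or more would have power 0.8816 fixed and 0.8485 with the futility rule.

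**The case against.** The strongest reply is that nothing in 10.2 is miscalculated: the section names a fixed exact test and gives its power correctly. Section 10.3 then discloses the rule, the boundaries and the 0.079 early stopping, so the effect is not hidden. The loss is 2.5 points and type I error falls slightly. Because 6 Phase I patients count towards the 60, the first effective look may be at 10 patients, and power is then 80.1%. The cut-off of 33 can be recovered from the 82%, and the Clopper-Pearson interval agrees with it. The toxicity figures rest on independence and on which version of the boundaries is applied, and at 30% true toxicity a stop is the safety rule doing its job.

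Much of this stands. It is a reporting gap, not a broken design, and the toxicity figures are illustrative only. It does not remove the point. Table 9 gives stopping probabilities, not power, and the reader cannot subtract one from the other: stopping is 8.15% but the power loss is 2.5 points, because most stopped trials would have missed 33 anyway. The alternative first look still gives about 80%, not 82%. A decision rule for the primary endpoint should be stated, not inferred from a power figure, particularly as 10.4 names no interval method.

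**Conclusion.** The concern holds. The 82% is the power of a fixed 60-patient test with success at 33 or more. Under the futility rule in 10.3 it is 79.7% with looks from the fifth patient, or 80.1% if the first look falls at 10. This assumes that the rule is followed as worded and that toxicity stops nothing. With toxicity stops at the Table 11 rates and independence from response, it is about 79% at 20% true toxicity and 73% at 30%; those two figures show direction and rough size only. One-sided type I error stays well under 0.025. The success count is unwritten, and the call at 32 of 60 depends on an unspecified choice of p-value or interval. The change should be made, but the sample size does not depend on it.

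**What to change.** Make two changes in 10.2:

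1. State that the Phase II efficacy criterion is met with at least 33 responders among 60 patients. This is the cut-off that the 82% already implies, it agrees with an exact (Clopper-Pearson) 95% interval, and it settles 32 of 60.
2. Replace the power statement with: about 80% at a true ORR of 60% with the Table 8 futility rule, not counting stops for toxicity (82% without interim stopping).

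The cost is two sentences. Sample size, stopping boundaries and type I error control do not change. The only downside is a slightly less favourable stated power.

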10.3 Statistical Design

Phase I

. In phase I portion of the study the MTD is defined as the highest daily oral dose evaluated at which $<33\%$ of patients experience a DLT. Six patients will be treated. If clinically significant drug related Grade 3-4 toxicity is observed during the first cycle in 0-1 patient out of 6 patients, this will define a safe schedule and the study will open broadly for the Phase II portion. If drug related Grade 3-4 toxicity is observed in 2 or more of 6 patients, this dose will exceed DLT, and a lower dose schedule will be investigated in an additional 6 patients. Please refer to Section 4.4. The dosing algorithm is presented in Table?.

Table 7. Dosing algorithm

Dose Level	Vosaroxin D1&D4	Decitabine
-3	50mg/mL	20 mg/m ² (Days 1-4)
-2	50 mg/m ²	20 mg/m ² (Days 1-5)
-1	70 mg/m ²	20 mg/m ² (Days 1-5)
0	90mg/m ²	20 mg/m ² (Days 1-5)

Phase II

Efficacy

The historical data suggested an ORR of 40% and with the assumption that the improved ORR is 60% the study will be stopped early if the observed patients' data suggest that:

$$\Pr(n > 0.6J \text{ data}) < 0.025$$

Here n is the overall response rate (ORR). That is, if at any time during the study we determine that there is a less than 2.5% chance that the average ORR is greater than 60%, we will terminate the study. The ORR is assumed to follow a non-informative prior of Beta (1.2, 0.8). The stopping boundaries for ORR, based on these assumptions and monitoring conditions are found in table 8. We will apply these stopping boundaries starting from the fifth patient and in cohorts of 5. For example, accrual will cease if only 2 or less than 2 patients experience overall response among the first 10 patients treated. The operating characteristics are summarized in table 8.

Table 8. Stopping boundaries for ORR

Number of patients evaluated	5	10	15	20	25	30	35	40	45	50	55	60
------------------------------	---	----	----	----	----	----	----	----	----	----	----	----

for response												
Number of patients with response (i.e., CR, CRp or CRi)	0	0-2	3-5	6-7	8-9	10-12	13-15	13-17	18-20	21-22	23-25	26-28

Table 9. Operating characteristics for monitoring of overall response rate

True overall Response Rate	Early Stopping Probability		Sample size		
			25%, 50%, 75%		
0.35	0.974		10	15	30
0.40	0.888		15	20	35
0.45	0.702		15	35	60
0.50	0.442		30	60	60
0.55	0.209		60	60	60
0.60	0.079		60	60	60
0.65	0.027		60	60	60

Toxicity Monitoring

Following are the rules for the monitoring of toxicities in the Phase II portion of the study. Toxicity will be defined as clinically significant non-hematologic drug related grade 3 or higher adverse events. The probability of toxicity is denoted by PE. We assume PE – beta (0.6, 1.4). Our stopping rule is given by the following probability statement: Probability (PE > 0.30 | data) > 0.975. That is, we will stop the study if, at any time during the study, we determine that there is more than 97.5% chance that the toxicity is more than 30%. This stopping rule will be applied in each cohort. The stopping boundaries for clinically significant toxicities observed during the first cycle, based on these assumptions and monitoring conditions found in table 10. We will apply these stopping boundaries starting from the fifth patient and in cohorts of 5. For example, accrual will cease if 4 patients experience clinically significant toxicities during the first cycle among the first 5 patients treated. The operating characteristics are summarized in table 11.

Table 10. Stopping boundaries for Phase II toxicities

The number of patients evaluated for toxicities	5	10	15	20	25	30	35	40	45	50	55	60
The number of patients with DLTs	4	5-6	7-8	9-10	11-12	13-14	15-16	17-18	19	20-21	22-23	24-25

Table 11. Operating characteristics

True Toxicity Rate	Early Stopping Probability	Sample Size		
		25 th percentile	Median	75 th percentile
0.10	0.008	60	60	60
0.20	0.010	60	60	60
0.30	0.082	60	60	60
0.40	0.474	30	60	60
0.50	0.906	15	25	40

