In the initial portion (Phase I) we will treat 6 patients with vosaroxin administered intravenously on days 1 and 4 at a dose of 90 mg/m^2 in the first cycle (induction 1) for a total dose of $180 \text{ mg/m}^2/\text{cycle}$ in combination with decitabine at a dose of 20 mg/m^2 intravenously for 5 consecutive days (Days 1 to 5). These doses have been given safely in previous studies as follows. A vosaroxin dose of 90 mg/m^2 was identified as the MTD in the dose-escalation (phase Ib) of the SP0-0012 study. In the phase II of this study 69 patients who had either first relapsed AML (relapse following an initial CR ≥ 3 months and ≤ 24 months) or primary refractory AML (failed to achieve a CR or CRp [CR with incomplete platelet recovery] following 1 or more cycles of induction, or an initial CR < 3 months) were treated with 80 or 90 mg/m^2 vosaroxin on days 1 and 4 in combination with cytarabine either as a continuous intravenous (CIV) infusion ($400 \text{ mg/m}^2/\text{day}$) on days 1-5 or a 2-hour intravenous (IV) infusion ($1 \text{ g/m}^2/\text{day}$) on days 1-5. The combination of vosaroxin at a dose of 90 mg/m^2 and IV cytarabine was well tolerated. Data from the SP0-0012 study provide the preliminary safety and clinical activity information for combination treatment, and formed the basis for the pivotal phase III VALOR study of vosaroxin in combination with cytarabine which is currently ongoing. Decitabine has been approved for treatment of MDS and AML at a dose of $20 \text{ mg/m}^2/\text{day}$ for days 1-5. Decitabine is less cytotoxic, less myelosuppressive and has lower incidence of mucositis than IV cytarabine which has safely been administered in combination with vosaroxin in the SP0-0012 and VALOR studies. Therefore, we anticipate that a starting dose of vosaroxin administered intravenously on days 1 and 4 at a dose of 90 mg/m^2 in the first cycle (induction 1) for a total dose of $180 \text{ mg/m}^2/\text{cycle}$ in combination with decitabine at a dose of 20 mg/m^2 intravenously for 5 consecutive days (Days 1 to 5) would be a reasonable option. These doses have been given safely in previous studies. The purpose of the lead-in phase I portion is to ensure safety. If clinically significant, study drug related grade 3-4 toxicity is observed during the first cycle in 1 or less of 6 evaluable patients treated, the study will transit to the Phase II portion. If clinically significant, study drug related grade 3-4 toxicity is observed during the first cycle in 2 or more of 6 evaluable patients treated, six additional patients will be treated on the Phase I portion at a lower dose level (see section 4.4 and section 10.2) until we define a Phase II safe dose schedule at which 1 or less out of 6 evaluable patients on the Phase I experience clinically significant, study drug related grade 3-4 toxicity during the first cycle. After the Phase I portion ensures safety thereby defining the Phase II dose schedule, all subsequent patients will receive the same dose schedule in the Phase II portion. This Phase II portion will include up to a total of 60 evaluable patients.

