Patients, who have not achieved remission (CR, CRp, Cri) following the initial induction (induction 1) course, can receive one additional induction course (induction 2) at the same dose as induction 1 to optimize response if indicated. The re-induction must be given within 4-8 weeks of documented refractory leukemia. Re-induction (Induction 2) may be given beyond the stipulated 8 weeks if approved by the study PI.

If the bone marrow aspirate and/or biopsy(s) performed after the induction courses reveal a remission marrow (CR/CRp/CRi), then the patient may proceed to consolidation therapy at the discretion of the treating investigator. In addition, any clinically significant drug-related, nonhematologic toxicity experienced by a patient should return to < grade 2 or the baseline grade before the patient continues treatment.

Should the patient not achieve CR/CRp/CRi after the second induction course, they will be taken off study unless clinical benefit is observed and the PI approves continuation of therapy on the protocol.

Hydroxyurea 1.5 g orally daily for up to 10 days is allowed in the first induction course for white blood count $>30.0 \times 10^9/L$.

4.4 Definition of Dose Limiting Toxicities and Criteria in Phase I:

Dose limiting toxicities will be according to the NCI CTEP criteria Common Terminology Criteria for Adverse Events version 4.0[44]. A non-hematologic dose-limiting toxicity (DLT) is defined as a clinically significant (as assessed by treating physician) grade 3 or 4 adverse event or abnormal laboratory value (according to CTCAE criteria) assessed by treating physician as related to study drug (and unrelated to disease progression, intercurrent illness, or concomitant medications) occurring during the first 28 days on study. A hematologic DLT is defined as severe myelosuppression with a hypoplastic marrow with less than 5% cellularity and no evidence of leukemia 42 days from start of therapy. This will define severe and delayed myelosuppression not related to persistent leukemia and likely related to treatment.

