4.7.4 Dose Modifications

Dose Modifications

Dose Level	Vosaroxin	Decitabine
	D1 & D4	
-3	50 mg/m ²	20 mg/m ² (Days 1 - 3)
-2	50 mg/m ²	20 mg/m ² (Days 1 -4)

-1	50 mg/m ²	20 mg/m ² (Days 1-5)
0	70mg/m ²	20 mg/m ² (Days 1-5)

4.7.5 Supportive Care:

Supportive care measures including blood products, infection prophylaxis and growth factors will be administered according to institutional and Leukemia Department guidelines.

4.7.6 Concomitant Medications:

Concomitant medications are recommended as prophylaxis for nausea, vomiting, and infections, and are allowed for managing myelosuppression as shown in Table 6. Myelosuppression is expected in patients with AML due to underlying disease, as well as due to chemotherapy (such as vosaroxin and decitabine), or both. Most patients have neutropenia, thrombocytopenia, or both at study entry. Myelosuppression may be managed with growth factor support and blood transfusion according to institutional standard of care, American Society of Clinical Oncology (ASCO) Practice Guidelines, and NCCN Practice Guidelines.

Infections secondary to myelosuppression are common in patients with AML, and may be related to underlying disease, chemotherapy, or both. Therefore, the use of prophylactic antibiotics, antifungal agents, and antiviral agents is recommended. A suggested regimen is ciprofloxacin (500 mg po q 12h), fluconazole (200 mg po qd), and acyclovir (800 mg po q 12h). One dose of prophylactic intrathecal chemotherapy will be allowed with diagnostic lumbar puncture.

All ongoing medications and therapies (including herbal products, nutritional supplements, and nontraditional medications) at screening will be considered prior medications. Concomitant medication data will not be collected or entered into the case report form; however, the subject's medication record will contain a list of concomitant medications. Patients will discontinue study treatment if they intentionally receive or require treatment with a medication prohibited by the protocol. If however prohibited medication is inadvertently administered/ taken by the patient, the patient may remain on study as long as the prohibited medication is discontinued as soon as feasible. End-of-treatment procedures will be performed, and follow-up will commence. Prohibited medications are shown in Table 6.

Table 6: Instructions for the use of concomitant medications and therapies

Category of Use	Medication	Comment on Use	Restriction on Use

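### The Phase I dose decision counts different events in Sections 3.2, 4.4 and 10.3, and the two branches within 10.3 can both be met by the same six patients

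*Combined protocol and SAP*

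**What the plan says.** All places use the same count rule: 0-1 of 6 opens Phase II, and 2 or more of 6 sends the next six patients to a lower dose level. The event that is counted differs.

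- **Section 10.3, open branch:** "If clinically significant drug related Grade 3-4 toxicity is observed during the first cycle in 0-1 patient out of 6 patients".
- **Section 10.3, lower-dose branch:** "If drug related Grade 3-4 toxicity is observed in 2 or more of 6 patients, this dose will exceed DLT". Clinical significance and the first-cycle limit are both absent. The sentence is followed by "Please refer to Section 4.4" and then the dosing table. The same section also ties the MTD to DLTs in fewer than 33% of patients.
- **Section 3.2:** the open branch begins "If clinically significant, study drug related grade 3-4 toxicity is observed during the first cycle in 1 or less of 6 evaluable patients treated", and the lower-dose branch uses the same event ("study drug related grade 3-4 toxicity is observed during the first cycle in 2 or more of 6 evaluable patients treated"). Neither branch excludes haematologic events. A pointer to 4.4 stands beside the mention of a lower dose level.
- **Section 4.2 (Treatment Plan in Phase I and II):** first-cycle DLT, with 28 days of assessment for non-haematologic and 42 days for haematologic toxicity.
- **Section 4.4:** first-cycle DLT in both branches. A non-haematologic DLT is a clinically significant, drug-related grade 3 or 4 event in the first 28 days. For blood and marrow, "A hematologic DLT is defined as severe myelosuppression with a hypoplastic marrow with less than 5% cellularity", with no evidence of leukaemia, 42 days from the start of therapy.

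**The concern.** A go/no-go rule works only if its branches are mutually exclusive and exhaustive, which requires both to count the same event over the same period. Here they do not. Within 10.3 the lower-dose branch is wider than the open branch, so one cohort can satisfy both. Across sections, ordinary grade 3-4 cytopenia attributed to treatment can count under 3.2 and 10.3 but not under 4.4, and the observation period is a first cycle of unstated length in one place and 28 or 42 days in another.

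The rule sets the MTD. By 10.2, six patients treated at the MTD are also counted among the 60 Phase II patients, so the ambiguity reaches the group in which the primary endpoint is assessed.

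**Working it through.** **1. The plan's own cut-off.** 1/6 = 16.7%, below 33%; 2/6 = 33.3%, not below 33%. The count rule agrees with the MTD definition in 10.3. The fault lies in what is counted, not in the cut-off.

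**2. Section 10.3 alone.** Suppose two of six patients have drug-related grade 3 laboratory changes judged not clinically significant, and nobody has a clinically significant event. The open branch counts 0 of 6 and is met. The lower-dose branch counts 2 of 6 and is also met. No assumed rate is needed.

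**3. Sections set side by side.**

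| Two of six patients have | 3.2 | 10.3 | 4.4 |
|---|---|---|---|
| Clinically significant, drug-related grade 4 neutropenia, marrow recovered by day 42 | 2/6, lower dose | 2/6, lower dose | 0/6, open |
| Clinically significant, drug-related non-haematologic grade 3 event after day 28, still in cycle 1 | 2/6, lower dose | 2/6, lower dose | 0/6, open |
| Hypoplastic marrow, under 5% cellularity, no leukaemia at day 42 | could be missed | could be missed | 2/6, lower dose |

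The second row needs a first cycle longer than 28 days. The Phase I text fixes no cycle length; 4.5, which concerns Phase II, has treatment repeated every 4-7 weeks. In the third row, the marrow criterion is not expressed as a toxicity grade, so a count of grade 3-4 events need not capture it.

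**4. Size, as illustration only.** Assumptions:

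- 4.4 DLT rate d = 10%, 15% or 20%. The documents give no rate.
- Rate of any counted grade 3-4 event a = 34%, 43% or 53%. These are the febrile neutropenia rates in Table 5 (2-hour infusion, combined, continuous infusion), from vosaroxin with cytarabine in relapsed or refractory AML. The partner drug and population differ, and the rates are not restricted to drug-related events.
- Every DLT is also a counted grade 3-4 event (subset), and patients are independent.

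For event rate p, P(0-1 of 6) = (1-p)^6 + 6p(1-p)^5. For p = 0.10 this is 0.531 + 0.354 = 0.886.

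| p | 0.10 | 0.15 | 0.20 | 0.34 | 0.43 | 0.53 |
|---|---|---|---|---|---|---|
| P(0-1 of 6) | 0.886 | 0.776 | 0.655 | 0.338 | 0.190 | 0.084 |
| P(2 or more of 6) | 0.114 | 0.224 | 0.345 | 0.662 | 0.810 | 0.916 |

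Under the subset assumption, at most one counted event implies at most one DLT. So P(opposite decisions) = P(0-1 DLTs) - P(0-1 counted events). For d = 10%, a = 34%: 0.886 - 0.338 = 0.548. From unrounded values:

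| | a = 34% | a = 43% | a = 53% |
|---|---|---|---|
| d = 10% | 0.55 | 0.70 | 0.80 |
| d = 15% | 0.44 | 0.59 | 0.69 |
| d = 20% | 0.32 | 0.47 | 0.57 |

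With one definition in both places, a = d and the difference is 0.

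**The case against.** The best defence is that the plan has only one DLT definition, in 4.4, and everything leads there. Section 10.3 defines the MTD through DLT and then refers to 4.4; 3.2 refers to it too; 4.2 uses first-cycle DLT. On this view the second sentence of 10.3 is a shortened complement of the fully qualified sentence before it. Cohort summaries also go to the IND Office at each step down and before Phase II opens, so no sentence is applied mechanically. Section 4.5 names a Phase II vosaroxin dose as an alternative to the MTD found in Phase I, citing current experience and another study, so the six-patient count is not the sole determinant.

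Much of this stands: DLT is a plausible intended trigger, and the review step limits the practical risk. But both pointers to 4.4 sit beside the lower-dose step and can be read as references to the dose levels. Neither says that 4.4 overrides the local wording, and the review step supplies no definition. The Phase II toxicity rule in 10.3 does specify non-haematologic events, which makes the omission from the Phase I rule visible.

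A reader might go further and infer that 10.3, read literally, would force a step down at every level because of expected myelosuppression, using all 24 Phase I patients without finding an MTD. The documents do not support that. Section 4.7.6 says "Myelosuppression is expected in patients with AML due to underlying disease, as well as due to chemotherapy", which gives no rate and names disease as well as treatment as the cause. Section 4.7.2 assumes low counts at diagnosis are due to disease, and every version of the trigger requires a relation to study drug. At an 80% event rate P(0-1 of 6) would be 0.002, but nothing in the documents supports such a rate. Nor does 3.2 count just any drug-related grade 3-4 toxicity: it requires clinical significance in both branches.

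**Conclusion.** The inconsistency is real and can be shown from the text alone. The two branches of 10.3 overlap, and 3.2 and 10.3 differ from 4.2 and 4.4 on haematologic events and on the observation window. The same six patients can therefore receive opposite decisions.

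How often this would happen cannot be derived from the documents. The range of about 0.32 to 0.80 depends on the assumed rates. It would shrink if febrile neutropenia were itself counted as a 4.4 DLT, or if many such events were attributed to disease. The subset assumption also leaves out disagreement in the other direction, where a day-42 marrow DLT is missed by a grade-based count. The conclusion is that the decision rule is defective as written, not that the trial would necessarily have reached a wrong dose.

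**What to change.** Reconcile 3.2, 4.2, 4.4 and 10.3 so that the open and lower-dose branches use one identical event definition and one set of observation windows. The text should state whether and how haematologic events count, and which section governs. Which definition to adopt is for the sponsor and the investigator.

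Section 4.5 speaks of current experience, which suggests that Phase I patients may already have been treated. If cohorts have been assessed, document which definition was applied to each.

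The cost is wording only; the count rule and sample size need not change.
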